Time to onset of ACR20/50 response will be estimated and presented using the Kaplan-Meier product-limit method for each treatment. Time to a given response will be defined as the length in weeks from Baseline until the first date when the response is achieved. Following derivation will be used: Days from Baseline until the first date divided by 7. There will be no rounding for the Kaplan Meier estimates. Subjects who discontinue study treatment prior to achieving a response will be censored at the date of study treatment discontinuation. Subjects who reach the Week 12 visit without achieving a response will be censored at the date of the Week 12 visit. Missing response data will be imputed with NRI.

...

Has been changed to

~~All other efficacy variables in the Double-Blind Period will be analyzed for all subjects in the FAS. For the Dose-Blind period, other efficacy variables will be analyzed for all subjects in the DBRS and ESS.~~

Other efficacy variables will be analyzed for all subjects in the FAS, DBRS, ESS, cDBRS, cESS, and DBS.

...

Time to onset of ACR20/50 response will be estimated and presented using the Kaplan-Meier product-limit method for each treatment. Time to a given response will be defined as the length in weeks from Baseline until the first date when the response is achieved. Following derivation will be used: Days from Baseline until the first date divided by 7. There will be no rounding for the Kaplan Meier estimates. Subjects who discontinue study ~~treatment~~ prior to achieving a response will be censored at the date of study ~~treatment~~ discontinuation. Subjects who reach the Week 12 visit without achieving a response will be censored at the date of the Week 12 visit. Missing response data will be imputed with NRI.

...

Section 10.1 Extent of exposure

The duration of exposure (in days) will be calculated as:

$$\begin{aligned} \text{Duration of exposure} \\ &= \text{Date of last injection} - \text{Date of first Injection} + 28 \end{aligned} \quad (16)$$

28 days refer to one half-life of bimekizumab. If a change of treatment occurs prior to completion of the dosing interval, duration of exposure to study medication will be calculated as:

$$\begin{aligned} \text{Duration of exposure} \\ &= \text{Date of treatment change} - \text{Date of first Injection} \end{aligned} \quad (17)$$

For subjects who have died the exposure will be as follows:

$$\text{Duration of exposure} = \text{Date of Death} - \text{Date of first Injection} + 1 \quad (18)$$

The sum over all duration of exposure (in years) will be calculated for the total subject-years of duration of exposure.

The duration of exposure will be summarized by treatment group using descriptive statistics. A by-subject listing of date of first and last dose and the duration of exposure will be performed.

Time at risk (in days) is defined as:

$$\text{Time at risk} = \text{Date of last injection} - \text{Date of first injection} + 140 \quad (19)$$

where 140 days refers to 5*half-life of bimekizumab.

The sum over all time at risk (in years) will be calculated for the total subject-years of time at risk.

The days on treatment and days on bimekizumab treatment will be calculated as follows:

$$\begin{aligned} \text{Days on treatment} & \\ &= \text{Date of last/latest dose} \\ &- \text{Date of first placebo or bimekizumab dose} + 1 \end{aligned} \quad (20)$$

$$\begin{aligned} \text{Days on bimekizumab treatment} & \\ &= \text{Date of last/latest dose} \\ &- \text{Date of first bimekizumab dose} + 1 \end{aligned} \quad (21)$$

Has been changed to

The duration of exposure (in days) will be calculated as:

$$\begin{aligned} \text{Duration of exposure} & \\ &= \text{Date of last injection} - \text{Date of first Injection} + 28 \end{aligned} \quad (16)$$

28 days refer to one half-life of bimekizumab. If a change of treatment occurs prior to completion of the dosing interval, duration of exposure to study medication will be calculated as:

$$\begin{aligned} \text{Duration of exposure} & \\ &= \text{Date of treatment change} - \text{Date of first Injection} \end{aligned} \quad (17)$$

For subjects who have died the exposure will be as follows:

$$\text{Duration of exposure} = \text{Date of Death} - \text{Date of first Injection} + 1 \quad (17+8)$$

The sum over all duration of exposure (in years) will be calculated for the total subject-years of duration of exposure.

The duration of exposure will be summarized by treatment group using descriptive statistics. A by-subject listing of date of first and last dose and the duration of exposure will be performed.

Time at risk (in days) is defined as:

$$\text{Time at risk} = \text{Date of last injection} - \text{Date of first injection} + 140 \quad (1819)$$

where 140 days refers to 5*half-life of bimekizumab.

The sum over all time at risk (in years) will be calculated for the total subject-years of time at risk.

The days on treatment and days on bimekizumab treatment will be calculated as follows:

$$\begin{aligned} \text{Days on treatment} &= \text{Date of last/latest dose} && (1920) \\ &- \text{Date of first placebo or bimekizumab dose} + 1 \end{aligned}$$

$$\begin{aligned} \text{Days on bimekizumab treatment} &= \text{Date of last/latest dose} && (2021) \\ &- \text{Date of first bimekizumab dose} + 1 \end{aligned}$$

Section 10.2.1 Exposure duration

The duration of each AE will be calculated as follows:

$$\text{Duration (days)} = \text{Date of outcome} - \text{Date of onset} + 1 \quad (22)$$

For the calculation of duration for AEs with missing start dates, the dates will be imputed as described in Section 4.2.2.

The time to first dose for each AE will be calculated as follows for all TEAEs:

$$\begin{aligned} \text{Time since first dose (days)} &= \text{Date of AE onset} - \text{Date of first dose} + 1 && (23) \end{aligned}$$

The time to most recent dose for each AE will be calculated as follows for all TEAEs:

$$\begin{aligned} \text{Time since most recent dose (days)} &= \text{Date of AE onset} && (24) \\ &- \text{Date of most recent dose prior to AE} + 1 \end{aligned}$$

Time to first dose and time to most recent dose will not be calculated for pretreatment AEs.

For the calculation of time to first bimekizumab and time to most recent bimekizumab dose the same formulas as above (20 and 21) will be used but the date of first bimekizumab dose will be used instead of the date of first dose. The time to first dose and time to first bimekizumab dose differs only for those subjects who receive placebo at Baseline.

Has been changed to

The duration of each AE will be calculated as follows:

$$\text{Duration (days)} = \text{Date of outcome} - \text{Date of onset} + 1 \quad (2122)$$

For the calculation of duration for AEs with missing start dates, the dates will be imputed as described in [Section 4.2.2](#).

The time to first dose for each AE will be calculated as follows for all TEAEs:

$$\begin{aligned} \text{Time since first dose (days)} \\ = \text{Date of AE onset} - \text{Date of first dose} + 1 \end{aligned} \quad (2223)$$

The time to most recent dose for each AE will be calculated as follows for all TEAEs:

$$\begin{aligned} \text{Time since most recent dose (days)} \\ = \text{Date of AE onset} \\ - \text{Date of most recent dose prior to AE} + 1 \end{aligned} \quad (2324)$$

Time to first dose and time to most recent dose will not be calculated for pretreatment AEs.

For the calculation of time to first bimekizumab and time to most recent bimekizumab dose the same formulas as above (2220 and 2321) will be used but the date of first bimekizumab dose will be used instead of the date of first dose. The time to first dose and time to first bimekizumab dose differs only for those subjects who receive placebo at Baseline.

Section 10.2.2 Exposure adjusted incidence rate (EAIR) and exposure adjusted event rate (EAER)

The EAIR is defined as the number of subjects (n) with a specific AE adjusted for the exposure and will be scaled to 100 patient-years:

$$EAIR = 100 * \frac{n}{\sum_{i=1}^n T_{Exp,i}} \quad (25)$$

where $T_{Exp,i}$ is a subject's exposure time in years up to the first occurrence of the AE of interest (equation [21] in years) at the level of coding evaluated.

If a subject has multiple events at the level of coding evaluated, the time of exposure is calculated to the first occurrence of the AE of interest. If a subject has no events, the total time at risk (15) is used.

Exact Poisson 95% CIs for incidence rates are calculated using the relationship between the Poisson and the Chi-square distribution (Ulm, 1990; Fay and Feuer, 1997):

$$LCL = \frac{\chi_{2n,\frac{\alpha}{2}}^2}{2} \quad (26)$$

$$UCL = \frac{\chi_{2(n+1),1-\frac{\alpha}{2}}^2}{2} \quad (27)$$

where n is the number of subjects with a specific AE for the incidence rate of interest and is the basis for the number of the degrees of freedom for the chi-square quantile for the upper tail probability χ^2 .

The EAER will be the number of AEs including repeat occurrences in individual subjects divided by the total time at risk scaled to 100 patient-years and calculated using:

$$EAER = 100 * \frac{N_{AE}}{\sum_{i=1}^n T_{Risk,i}} \quad (28)$$

where N_{AE} is the total number of AEs and $T_{Risk,i}$ is a subject's total time at risk in years.

No CI will be computed for EAER.

Has been changed to

The EAIR is defined as the number of subjects (n) with a specific AE adjusted for the exposure and will be scaled to 100 patient-years:

$$EAIR = 100 * \frac{n_{AE}}{\sum_{i=1}^{n_{AE}} T_{Exp,i} + \sum_{j=1}^{n_{noAE}} T_{Risk,j}} \quad (2425)$$

where $T_{Exp,i}$ is a subject's exposure time in years up to the first occurrence of the AE of interest (equation [21] in years) at the level of coding evaluated, **n_{noAE} the number of subjects without the specific AE and $T_{Risk,j}$ the total time at risk scaled to 100 patient-years (equation [18] in years).**

If a subject has multiple events at the level of coding evaluated, the time of exposure is calculated to the first occurrence of the AE of interest. If a subject has no events, the total time at risk (**1815**) **in years** is used.

Exact Poisson 95% CIs for incidence rates are calculated using the relationship between the Poisson and the Chi-square distribution (Ulm, 1990; Fay and Feuer, 1997):

$$LCL = \frac{\chi_{2n,\alpha}^2}{2} \quad (2526)$$

$$UCL = \frac{\chi_{2(n+1),1-\alpha/2}^2}{2} \quad (2627)$$

$$CI_{Lower} = 100 * \frac{LCL}{\sum_{i=1}^{n_{AE}} T_{Exp,i} + \sum_{j=1}^{n_{noAE}} T_{Risk,j}} \quad (27)$$

$$CI_{Upper} = 100 * \frac{UCL}{\sum_{i=1}^{n_{AE}} T_{Exp,i} + \sum_{j=1}^{n_{noAE}} T_{Risk,j}} \quad (28)$$

where n is the number of subjects with a specific AE for the incidence rate of interest and is the basis for the number of the degrees of freedom for the chi-square quantile for the upper tail probability χ^2 , **$T_{Exp,i}$ is a subject's exposure time in years up to the first occurrence of the**

AE of interest (equation [21] in years) at the level of coding evaluated, n_{noAE} the number of subjects without the specific AE and $T_{Risk,j}$ the total time at risk scaled to 100 patient-years (equation [18] in years).

The EAER will be the number of AEs including repeat occurrences in individual subjects divided by the total time at risk scaled to 100 patient-years and calculated using:

$$EAER = 100 * \frac{N_{AE}}{\sum_{j=1}^{n_{All}} T_{Risk,j}} \quad (2928)$$

where N_{AE} is the total number of AEs and $T_{Risk,j}$ is a subject's total time at risk in years **and n_{All} the number of subjects.**

No CI will be computed for EAER.

Section 10.3 Clinical laboratory evaluations

...

Different summary tables for hematology and biochemistry variables will be provided: observed values and change from Baseline, from Baseline to maximum post-Baseline value, from Baseline to minimum post-Baseline value, shift from Baseline to end of treatment, shift from Baseline to end of double-blind treatment, and markedly abnormal laboratory data.

...

Table 13-1: Laboratory measurements

Hematology	Biochemistry	Urinalysis
Basophils	Calcium	Albumin
Eosinophils	Chloride	Bacteria
Lymphocytes	Magnesium	Crystals
Atypical lymphocytes	Potassium	Glucose
Monocytes	Sodium	pH
Neutrophils	Glucose	RBC
Hematocrit	BUN	WBC
Hemoglobin	Creatinine	Urine dipstick for pregnancy testing ^b
MCH	hs-CRP/CRP ^a	
MCHC	AST	
MCV	ALT	
Platelet count	GGT	
RBC count	ALP	

Table 13–1: Laboratory measurements

Hematology	Biochemistry	Urinalysis
WBC count	Total bilirubin	
	LDH	
	Total cholesterol	
	Serum pregnancy testing ^b	

ALP=alkaline phosphatase; ALT=alanine aminotransferase; AST=aspartate aminotransferase; BUN=blood urea nitrogen; CRP=C-reactive protein; GGT=gamma glutamyltransferase; hs-CRP=high sensitivity C-reactive protein; LDH=lactate dehydrogenase; MCH=mean corpuscular hemoglobin; MCHC=mean corpuscular hemoglobin concentration; MCV=mean corpuscular volume; RBC=red blood cell; SFU=Safety Follow-up; WBC=white blood cell

^a Both CRP and hs-CRP will be tested at specified visits per Protocol Table 5.1.

^b A serum pregnancy test will be performed at Screening for all women of childbearing potential. This recommendation also applies to women of childbearing potential with infrequent or irregular menstrual cycles and women during menopause. Natural menopause is recognized to have occurred after 12 consecutive months of amenorrhea, for which there is no other obvious pathological or physiological cause (International Menopause Society, 2015). A urine pregnancy test is also required at the Baseline, Week 48, ET, and at SFU visits. A urine pregnancy test will also be performed at any study visit where there has been a delay in menses. This recommendation also applies to women of childbearing potential with infrequent or irregular menstrual cycles. Pregnancy test results must be negative prior to administering IMP.

Has been changed to

...

Different summary tables for hematology and biochemistry variables will be provided, **based on data from scheduled visits**: observed values and change from Baseline, from Baseline to maximum post-Baseline value, from Baseline to minimum post-Baseline value, shift from Baseline to end of treatment, ~~shift from Baseline to end of double blind treatment~~, and markedly abnormal laboratory data.

End of treatment will be defined as the Week 48 visit or the early termination assessment depending if the subject discontinued early or not.

...

Table 13–1: Laboratory measurements

Hematology	Biochemistry	Urinalysis
Basophils	Calcium	Albumin
Eosinophils	Chloride	Bacteria
Lymphocytes	Magnesium	Crystals
Atypical lymphocytes	Potassium	Glucose
Monocytes	Sodium	pH

Table 13–1: Laboratory measurements

Hematology	Biochemistry	Urinalysis
Neutrophils	Glucose	RBC
Hematocrit	BUN	WBC
Hemoglobin	Creatinine	Urine dipstick for pregnancy testing ^b
MCH	hs-CRP/CRP ^a	
MCHC	AST	
MCV	ALT	
Platelet count	GGT	
RBC count	ALP	
WBC count	Total bilirubin	
	LDH	
	Total cholesterol	
	Albumin	
	Serum pregnancy testing ^b	

ALP=alkaline phosphatase; ALT=alanine aminotransferase; AST=aspartate aminotransferase; BUN=blood urea nitrogen; CRP=C-reactive protein; GGT=gamma glutamyltransferase; hs-CRP=high sensitivity C-reactive protein; LDH=lactate dehydrogenase; MCH=mean corpuscular hemoglobin; MCHC=mean corpuscular hemoglobin concentration; MCV=mean corpuscular volume; RBC=red blood cell; SFU=Safety Follow-up; WBC=white blood cell

^a Both CRP and hs-CRP will be tested at specified visits per Protocol Table 5.1.

^b A serum pregnancy test will be performed at Screening for all women of childbearing potential. This recommendation also applies to women of childbearing potential with infrequent or irregular menstrual cycles and women during menopause. Natural menopause is recognized to have occurred after 12 consecutive months of amenorrhea, for which there is no other obvious pathological or physiological cause (International Menopause Society, 2015). A urine pregnancy test is also required at the Baseline, Week 48, ET, and at SFU visits. A urine pregnancy test will also be performed at any study visit where there has been a delay in menses. This recommendation also applies to women of childbearing potential with infrequent or irregular menstrual cycles. Pregnancy test results must be negative prior to administering IMP.

...

Table 10-4 updated to align with Table 12-4 from the Protocol Amendment 2.

Table 10-5 updated to align with Table 12-5 from the Protocol Amendment 2.

Section 12.2 Calculation rules for duration of adverse events

The calculation rules for duration of AEs are presented in Table 12–2. AE duration is computed and reported in day.

Table 13–2: Calculation rules for duration of adverse events

Data Availability	Onset Date	Outcome Date	Calculation Rules
Complete data	D1	D2	Duration = D2 – D1 + 1
Start date missing	-	D2	Duration = < D2 – D0 Where, for a subject in the FAS, D0 is the date of the first intake of IMP, and for screen failures, D0 is the date of the Screening visit day
End date missing	D1	-	Duration = > Discharge day – D1 For resolved and ongoing AE Duration Where discharge refers to the date of Visit 16 (Week 48) or date of discontinuation
Start and end date missing	-	-	Duration = > Discharge day – D0 For resolved and ongoing AE Duration Where, for a subjects in the FAS, D0 is the date of the first intake of IMP, and for screen failures, D0 is the date of the Screening visit day, Discharge refers to the date of Visit 16 (Week 48) or date of discontinuation.

Has been changed to

The calculation rules for duration of AEs are presented in [Table 12–2](#). AE duration is computed and reported in day.

Table 13–3: Calculation rules for duration of adverse events

Data Availability	Onset Date	Outcome Date	Calculation Rules
Complete data	D1	D2	Duration = D2 – D1 + 1
Start date missing	-	D2	Duration = < D2 – D0 + 1 Where, for a subject in the SSFAS , D0 is the date of the first intake of IMP, and for screen failures, D0 is the date of the Screening visit day
End date missing	D1	-	Duration = > Final contact date Discharge day – D1 + 1 For resolved and ongoing AE Duration Where discharge refers to the date of Visit 16 (Week 48) or date of discontinuation

Table 13–3: Calculation rules for duration of adverse events

Data Availability	Onset Date	Outcome Date	Calculation Rules
Start and end date missing	-	-	Duration = > Final contact date Discharge day – D0 + 1 For resolved and ongoing AE Duration Where, for a-subjects in the SSFAS , D0 is the date of the first intake of IMP, and for screen failures, D0 is the date of the Screening visit day, Discharge refers to the date of Visit 16 (Week 48) or date of discontinuation.

This document cannot be used to support any marketing authorization application and any extensions or variations thereof.
 REDACTED COPY

13.5 Amendment 5

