### 15.3.2.2 Analysis of the other efficacy variables

All other efficacy variables in the Double-Blind Period will be analyzed for all subjects in the FAS. For the Dose-Blind period, other efficacy variables will be analyzed for all subjects in the DBRS and ESS.

All categorical variables will be summarized using frequency tables by each visit.

All continuous variables will be summarized using descriptive statistics by each visit.

Time to onset of ACR20/50 response will be estimated and presented using the Kaplan-Meier product-limit method for each treatment. Time to a given response will be defined as the length in days from Baseline until the first date when the response is achieved. Subjects who discontinue study treatment prior to achieving a response will be censored at the date of study treatment discontinuation. Subjects who reach the Week 12 visit without achieving a response will be censored at the date of the Week 12 visit.

The median time to response including the two-sided 95% confidence interval (CI) will be calculated for each treatment. Between group differences (each bimekizumab dose versus placebo) will be analyzed with the log-rank statistic.

All other efficacy variables will be analyzed using observed cases as treated and imputed with NRI for binary variables and multiple imputation for categorical/continuous variables (see Section 15.7).

Subjects in the ESS who discontinue with bimekizumab treatment during the Dose-Blind Period will be treated as missing and categorical/continuous variables will be imputed.

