2.2.1.3 Other efficacy variables

Other efficacy variables will be assessed as specified in [Table 2-1](#):

- Time to ACR20 and ACR50 response

- Psoriasis Area and Severity Index 100% (PASI100) response in the subgroup of subjects with psoriasis involving at least 3% of BSA at Baseline/Day 1
- ACR20, ACR50, and ACR70 response
- Composite endpoint comprised of ACR50 and PASI90 response in the subgroup of subjects with psoriasis involving at least 3% of BSA at Baseline/Day 1
- Minimal Disease Activity (MDA) and modified MDA
- Change from Baseline in the Disease Activity Score-28 based on high sensitivity C-reactive protein (DAS28 [CRP])
- Change from Baseline in all individual American College of Rheumatology (ACR) score components:
 - SJC
 - TJC
 - Health Assessment Questionnaire—Disability Index (HAQ-DI)
 - Patient’s Assessment of Arthritis Pain (PtAAP)
 - Physician’s Global Assessment of Disease Activity (PhGADA)
 - Patient’s Global Assessment of Disease Activity (PGADA)
 - high sensitivity C-reactive protein (hs-CRP)
- Change from Baseline in the Bath Ankylosing Spondylitis Disease Activity Index (BASDAI)
- Change from Baseline in the modified Nail Psoriasis Severity Index (mNAPSI)
- Change from Baseline in the Maastricht Ankylosing Spondylitis Enthesitis (MASES) Index
- Change from Baseline in the Leeds Dactylitis Index (LDI)
- Psoriatic Arthritis Impact of Disease (PsAID)-9
- Psoriatic Arthritis Quality of Life (PsAQoL)
- Change from Baseline in Physical Component Summary (PCS) and Mental Component Summary (MCS) of the SF-36 (Short-Form 36-Item Health Survey)
- Change from Baseline in Hospital Anxiety and Depression Scale (HADS) HADS-Anxiety (A) and HADS-Depression (D) scores
- Percentage of subjects with scores below 8 in HADS-A and HADS-D (subjects with normal scores)

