3.6 Analysis sets

The primary efficacy variable will be analyzed for all subjects in the Full Analysis Set (FAS). The supportive analyses for the primary efficacy variables will include the Randomized Set (RS) and PPS. All other efficacy variables will be based on the FAS. Demographics tables will be performed for FAS, Safety Set (SS), and Dose-Blind Set (DBS). Safety variables will be summarized using the SS. In addition, safety analyses during the Dose-Blind Period will be conducted on all subjects in the DBS. PK variables will be analyzed for all subjects in the PK-PPS. PD variables will be analyzed for all subjects in the PD-PPS.

At the time of the Week 48 interim it was discovered that the Dose-Blind Responder Set (DBRS) and Escape Subject Set (ESS) were defined incorrectly from the original intent. The original

intent of the ESS analysis set was to have only those subjects that were eligible to receive rescue therapy, that went on to actually receive rescue therapy, with all other subjects remaining in the DBRS. As such, two extra sets, the Corrected Dose-Blind Responder Set (cDBRS) and Corrected Escape Subject Set (cESS) have been added. These analysis sets will correctly select out those subjects that were eligible and received rescue medication. All outputs created on the DBRS and ESS will also be produced on the cDBRS and cESS to give full transparency of the difference. Further all outputs using the DBRS and ESS will be repeated on the DBS and this analysis will be used as the main analysis of the Dose-Blind as this analysis set is the most unbiased set.

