3.6.10 Dose-Blind Responder Set (DBRS)

The DBRS consists of all subjects who started the Dose-Blind Period and who received at least 1 dose of the IMP during the Dose-Blind Period and who have achieved at least a 10% reduction from Baseline in SJC and TJC at Week 16, Week 24, and Week 36.

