8.3 Analysis of other efficacy variables

All other efficacy variables will be analyzed for all subjects in the FAS, DBRS, ESS, cDBRS, cESS, and DBS.

All binary variables will be summarized using frequency tables by each visit. All continuous variables will be summarized using descriptive statistics by each visit.

The Hospital Anxiety and Depression Scale (HADS) will be analyzed separately for HADS-A and HADS-D. The summary statistics for HADS-A and HADS-D will be presented in two different tables.

Subgroup of subjects will be used for the analyses of mNAPSI, MASES, and LDI. The MASES will be analyzed for subjects with enthesitis at Baseline ($MASES > 0$). The LDI will be summarized for subjects with dactylitis at Baseline ($LDI > 0$) and the mNAPSI will be analyzed on a subgroup of subjects with nail disease at Baseline ($mNAPSI > 0$).

CDF plots of PSAID-9 change from Baseline to Week 12 and from Week 12 to Week 48 by treatment group will be presented as well as a frequency table with number of subjects with $PSAID-9 \leq 3$.

Times series plots will be provided for the response rate for the primary and secondary efficacy variables. The plots will show the weekly response rate over the first 12 weeks.

Time to onset of ACR20/50 response will be estimated and presented using the Kaplan-Meier product-limit method for each treatment. Time to a given response will be defined as the length in weeks from Baseline until the first date when the response is achieved. Following derivation will be used: Days from Baseline until the first date divided by 7. There will be no rounding for the Kaplan Meier estimates. Subjects who discontinue study prior to achieving a response will be censored at the date of study discontinuation. Subjects who reach the Week 12 visit without achieving a response will be censored at the date of the Week 12 visit. Missing response data will be imputed with NRI.

The median time to response including the two-sided 95% CI will be calculated for each treatment. Between groups differences (each bimekizumab dose versus placebo) will be analyzed using a log-rank test stratified by geographic region and prior TNF inhibitor exposure. Missing response data will be imputed with NRI.

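### SAP Section 8.3 gives the other efficacy variables six analysis sets and no period limit, so Week 12 time-to-response tests against placebo can run in sets defined by later response or rescue

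*SAP*

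**What the plan says.** Protocol Section 15.3.2.2 assigns populations by period: "All other efficacy variables in the Double-Blind Period will be analyzed for all subjects in the FAS", and then "For the Dose-Blind period, other efficacy variables will be analyzed for all subjects in the DBRS and ESS".

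The change log for SAP Amendment 4 (Section 13.4.2) shows the matching SAP sentences deleted and one sentence put in their place: "Other efficacy variables will be analyzed for all subjects in the FAS, DBRS, ESS, cDBRS, cESS, and DBS". The current SAP Section 8.3 reads: "All other efficacy variables will be analyzed for all subjects in the FAS, DBRS, ESS, cDBRS, cESS, and DBS". It names no period.

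SAP Section 2.2.1.3 lists "Time to ACR20 and ACR50 response" among these variables. SAP Section 8.3 ends follow-up for it at Week 12: "Subjects who reach the Week 12 visit without achieving a response will be censored at the date of the Week 12 visit". The same section tests each bimekizumab dose against placebo with a log-rank test stratified by region and prior TNF inhibitor exposure. It also plans cumulative distribution plots of the PsAID-9 change from Baseline to Week 12.

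The added sets are built from later events. The DBRS (SAP Section 3.6.10) takes Dose-Blind subjects "who have achieved at least a 10% reduction from Baseline in SJC and TJC at Week 16, Week 24, and Week 36". The ESS takes those who missed that threshold at one of these visits. The cESS and cDBRS also use receipt of rescue. The DBS requires only one dose in the Dose-Blind Period.

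SAP Section 3.6 still says: "All other efficacy variables will be based on the FAS".

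**The concern.** The endpoint is complete at Week 12, but membership of the DBRS, ESS, cDBRS and cESS is decided at Weeks 16, 24 and 36. Between the two, placebo and 16mg subjects are rerandomized to 160mg or 320mg (Protocol Section 5.1.3). In the 160mg, 320mg and loading-dose arms, later joint response is largely a continuation of the regimen being tested. In the placebo arm it is response to bimekizumab started at Week 12. A Week 12 comparison with placebo inside such a set therefore conditions on an outcome that means different things in the two arms, and the arms are no longer comparable by randomization.

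What is at stake is a group of extra p-values against placebo that look like repeats of the FAS analysis but do not estimate the same quantity. SAP Section 3.10, which lists departures from the protocol, records the change from days to weeks for this same endpoint but not the change of population.

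**Working it through.** **1. The texts side by side.**

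- Protocol 15.3.2.2: FAS for the Double-Blind Period; DBRS and ESS for the Dose-Blind Period.
- SAP 8.3 (current): six sets for every other efficacy variable, no period.
- SAP 3.6: other efficacy variables on the FAS. Outputs made on the DBRS and ESS are repeated on the cDBRS, cESS and DBS, and the DBS is the main analysis of the Dose-Blind Period.

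Sections 3.6 and 8.3 of the SAP cannot both be followed for a variable that ends at Week 12.

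**2. Number of log-rank tests.** There are 2 endpoints (ACR20, ACR50) and 4 bimekizumab arms against placebo, so 2 x 4 = 8 tests per set. Under the protocol's rule the total is 8. Under SAP 8.3 as written it is 6 x 8 = 48, which is 40 more: 4 x 8 = 32 in the DBRS, ESS, cDBRS and cESS, and 8 in the DBS.

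**3. Direction and size of the selection effect.** The documents give no figure for time to response, and no retention rates or correlations, so this part is an illustration. It uses Week 12 ACR50 status as a stand-in for time to first response.

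*Inputs from SAP Section 2.4.* Planning rates are 58.5% (320mg), 42.2% (160mg) and 8% (placebo). With 30% TNF-experienced subjects and a 25% relative reduction, the factor is 1 - 0.30 x 0.25 = 0.925. This gives 54.1%, 39.0% and 7.4%. (With these planning rates and 40 per arm, a normal-approximation trend test reproduces the stated power of >99%.)

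*Assumptions.* A share s = 0.80 of each arm is in the DBRS (range 0.70 to 0.90), and everyone else is treated as ESS. The latent correlation rho between Week 12 response and DBRS membership is 0.6 to 0.8 in the 160mg and 320mg arms and 0 to 0.4 in placebo.

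*Formulas*, with p the ACR50 rate and Phi2 the bivariate normal distribution function:

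- P(ACR50 given DBRS) = Phi2(z_p, z_s; rho) / s
- P(ACR50 given ESS) = (p - Phi2(z_p, z_s; rho)) / (1 - s)
- approximate hazard ratio of response = ln(1 - p_active) / ln(1 - p_placebo)

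*Results at s = 0.80:*

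| Comparison with placebo | FAS | DBRS | ESS |
|---|---|---|---|
| 160mg, difference (points) | 31.6 | 37.6 to 40.9 | -5.5 to 7.7 |
| 320mg, difference (points) | 46.7 | 54.0 to 58.5 | -0.5 to 17.7 |
| 160mg, approximate hazard ratio | 6.4 | 6.7 to 8.6 | 0.25 to 6.1 |
| 320mg, approximate hazard ratio | 10.1 | 10.7 to 14.0 | 0.94 to 13.5 |

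Two cells for 160mg as examples. DBRS with rho 0.6 (active) and 0.4 (placebo): 46.5% - 8.9% = 37.6 points. ESS with rho 0.8 and 0: 1.9% - 7.4% = -5.5 points. Over s = 0.70 to 0.90 the DBRS differences run from 35 to 47 points (160mg) and 51 to 65 points (320mg).

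*Sensitivity.* Giving placebo the lower correlation helps to produce the larger DBRS effect. With rho = 0.6 in both arms and s = 0.80, the 160mg hazard ratio in the DBRS is 6.5, essentially the FAS value. With rho = 0.7 in both arms, 80% of the 160mg arm kept and 60% of placebo kept, the DBRS rates are 47.5% and 12.1%. The difference rises to 35.4 points, but the hazard ratio falls to ln(0.525)/ln(0.879) = 5.0, against 6.4 in the FAS.

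**The case against.** The strongest reply is that the added sets were meant for the Dose-Blind Period only. SAP Sections 3.6 and 4.3.2.2 explain them as repeats of DBRS and ESS outputs, which under the protocol covered only that period, and call the DBS the main analysis there. The output shells are not among the documents, so 48 tests is the literal maximum and not an established count. The consequence is also small. The FAS analysis is kept. The endpoint is exploratory (Protocol Section 4.1.3) and outside the sequential testing in SAP Section 4.5. The Week 12 interim (SAP Section 4.3.1) already included time to response, and it preceded Amendments 3 and 4. The PsAID-9 plots carry no p-values.

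All of this stands, and it limits the importance of the point. It does not settle the text: a programmer who follows Section 8.3 would produce the extra tests, and Section 3.6 contradicts that section without overriding it.

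A reader might go further and infer that the rule inflates the drug effect. The documents do not support that. The ESS and cESS select nonresponders, the cDBRS keeps rescue-eligible subjects who were not rescued, and the DBS is not selected on joint response. Even in the DBRS the hazard ratio, which is the scale of the log-rank test, can fall. The 16mg arm switches at Week 12 as placebo does, so the contrast between continued and new treatment does not apply to it. With no drug effect, selection would be alike in the arms and would not by itself favour bimekizumab.

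**Conclusion.** The point holds as a defect in the rule for analysis sets. As written, SAP Section 8.3 permits Week 12 comparisons with placebo in four sets defined by post-switch response or rescue. This departs from Protocol Section 15.3.2.2, conflicts with SAP Section 3.6 and is not listed in SAP Section 3.10. The literal reading adds up to 40 log-rank tests to the 8 in the FAS, 32 of them in those four sets.

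The bias depends on the set. Under the assumed retention and correlations, the risk difference is larger in the DBRS and smaller or reversed in the ESS; the cESS selects in the same direction as the ESS. Neither the sign on the hazard-ratio scale nor the size can be fixed from the documents. No primary or multiplicity-controlled conclusion is affected. The correction is worth making because the extra comparisons have no valid reading as randomized evidence.

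**What to change.** Restore the split in SAP Section 8.3, for example:

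> Other efficacy variables in the Double-Blind Period, including time to ACR20 and ACR50 response, its log-rank tests and the PsAID-9 change to Week 12, are analyzed in the FAS only. Dose-Blind visits are summarized descriptively in the DBS (main), with the DBRS, ESS, cDBRS and cESS as supportive.

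Reword SAP Section 3.6 to agree, stating the period to which each set applies. In SAP Section 3.10, list whatever departure from Protocol Section 15.3.2.2 then remains, namely the use of the DBS, cDBRS and cESS for the Dose-Blind Period. The cost is SAP wording only. No data collection changes, and the number of outputs falls.
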